11.7.5 Permanent Discontinuation of Study Drug(s)

In the absence of acceptable enzyme level decrease or lack of a plausible alternative explanation for the elevated laboratory pattern, consider permanent discontinuation of study drug treatment.

11.7.6 Management Flow Chart

The following flow chart can be used to manage potential hepatotoxicity cases.

ALP = alkaline phosphatase; ALT = alanine aminotransferase; AST = aspartate aminotransferase; INR = international normalized ratio; TBL = total bilirubin; ULN = upper limit normal.

11.8 Appendix 8. Protocol-specific Anticipated Serious Adverse Events

Anticipated serious adverse events are events that are anticipated to occur in the study population at some frequency independent of investigational product exposure and do not need to be reported individually as a US FDA Investigational New Drug (IND) safety report by the sponsor. Identification and reporting of anticipated serious adverse events is the responsibility of the sponsor; the investigator is responsible for reporting adverse events and serious adverse events as described in Section 8.4.6 and Section 11.4.

Anticipated Serious Adverse Events for Study 20210004

MedDRA Preferred Term ^a
Cytokine release syndrome
Immune effector cell-associated neurotoxicity syndrome
Neutropenia

^aExact Preferred Term according to MedDRA Version 27.0

**11.9 Appendix 9. Eastern Cooperative Oncology Group (ECOG)
Performance Status and New York Heart Association (NYHA)
Functional Classification**

Eastern Cooperative Oncology Group (ECOG) Performance Status (PS)

- 0: Fully active, able to carry out all pre-disease performance without restriction.
- 1: Restricted in physically strenuous activity, but ambulatory and able to carry out work of a light or sedentary nature (eg, light housework, office work).
- 2: Ambulatory and capable of all self-care, but unable to carry out any work activities. Up and about more than 50% of waking hours.
- 3: Capable of only limited self-care, confined to bed or chair more than 50% of waking hours.
- 4: Completely disabled. Cannot carry out any self-care. Totally confined to bed or chair.
- 5: Dead

New York Heart Association (NYHA) Functional Classification

- Class I: No limitation of physical activity. Ordinary physical activity does not cause undue fatigue, palpitation, or dyspnea.
- Class II: Slight limitation of physical activity. Comfortable at rest, but ordinary physical activity results in fatigue, palpitation, or dyspnea.
- Class III: Marked limitation of physical activity. Comfortable at rest, but less than ordinary activity causes fatigue, palpitation, or dyspnea.
- Class IV: Unable to carry out any physical activity without discomfort. Symptoms of cardiac insufficiency may be present even at rest. If any physical activity is undertaken, discomfort is increased.

11.10 Appendix 10. Response Evaluation Criteria in Solid Tumors
Version 1.1 (RECIST 1.1); Eisenhauer et al, 2009**11.10.1 Definitions****11.10.1.1 Measurable Disease**

The presence of at least 1 measurable lesion. If the measurable disease is restricted to a solitary lesion, its neoplastic nature should be confirmed by cytology/histology.

11.10.1.2 Measurable Lesions**11.10.1.2.1 Measurable Non-nodal Tumor Lesions**

Non-nodal lesions with clear borders that can be accurately measured in at least 1 dimension with longest diameter ≥ 10 mm in computed tomography (CT)/magnetic resonance imaging (MRI) scan with slice thickness no greater than 5 mm. When slice thickness is greater than 5 mm, the minimum size of measurable lesion should be twice the slice thickness.

11.10.1.2.2 Nodal Lesions

Lymph nodes are to be considered measurable if ≥ 15 mm in short axis when assessed by CT/MRI (scan slice thickness recommended to be no greater than 5 mm). At baseline and in follow-up, only the short axis will be measured and followed.

11.10.1.2.3 Cystic Lesions

Cystic lesions thought to represent cystic metastases can be considered as measurable lesions, if they meet the definition of measurability described above for non-nodal lesions.

11.10.1.2.4 Bone lesions with identifiable soft tissue components

Bone lesions with identifiable soft tissue components, that can be evaluated by cross sectional imaging techniques such as CT or MRI can be considered as measurable lesions if the soft tissue component meets the definition of measurability described above for non-nodal lesions.

11.10.1.2.5 Clinically Measured Lesions

Visible or palpable lesions can be considered measurable if ≥ 10 mm in longest diameter for non-nodal or ≥ 15 mm in shortest diameter for lymph nodes. Lesions should be measured radiologically if more accurate, if not then measured by calipers.

11.10.1.2.6 Irradiated Lesions

Tumor lesions situated in a previously irradiated area, or in an area subjected to other loco-regional therapy, are not measurable unless there has been demonstrated progression that is measurable in the lesion prior to enrollment.

11.10.1.3 Non-measurable Lesions

All other lesions, including small lesions (longest diameter < 10 mm or pathological lymph nodes with ≥ 10 mm to < 15 mm short axis with CT scan slice thickness no greater than 5 mm) are considered non-measurable. (When slice thickness is greater than 5 mm, the minimum size of measurable lesion should be twice the slice thickness).

Other examples of lesions usually considered to be non-measurable include:

- Lesions with prior local treatment: tumor lesions situated in a previously irradiated area, or an area subject to other loco-regional therapy, should not be considered measurable unless there has been demonstrated progression in the lesion.
- Categorically, clusters of small lesions, bone lesions without a soft tissue component, inflammatory breast disease, ascites, pleural/pericardial effusions, lymphangitis cutis/pulmonitis and leptomeningeal disease are non-measurable.

11.10.2 Methods of Measurement

All measurements should be taken and recorded in metric notation, using a ruler or calipers. The same method of assessment and the same technique should be used to characterize each identified and reported lesion at baseline and throughout the trial.

Imaging-based evaluation is preferred to evaluation by clinical examination unless the lesion(s) being followed cannot be imaged but are assessable by clinical exam. Clinical lesions will be assessed using calipers (eg, skin nodules). In the case of skin lesions, documentation by color photography, including a ruler to estimate the size of the lesion, is recommended.

11.10.2.1 CT/MRI

Contrast-enhanced CT or MRI should be used to assess all lesions. Optimal visualization and measurement of metastasis in solid tumors requires consistent administration (dose and rate) of intravenous (IV) contrast as well as timing of scanning. CT and MRI should be performed with ≤ 5 mm thick contiguous slices. The longest diameter of selected lesions should be measured in the plane in which the images were acquired. Ideally, the same scanner or at least type of scanner should be used and the image acquisition protocol should be followed as closely as possible to prior scans.

11.10.2.2 PET-CT

At present, the low dose or attenuation correction CT portion of a combined positron emission tomography - computed tomography (PET-CT) is not always of optimal diagnostic CT quality for use with Response Evaluation Criteria in Solid Tumors (RECIST) measurements. However, if the site can document that the CT performed as part of a PET-CT is of identical diagnostic quality to a diagnostic CT (with IV and oral contrast), then the CT portion of the PET-CT can be used for RECIST measurements and can be used interchangeably with conventional CT in accurately measuring cancer lesions over time. Note, however, that the PET portion of the CT introduces additional data which may bias an investigator if it is not routinely or serially performed.

11.10.2.3 Ultrasound

Ultrasound is not useful in assessment of lesion size and should not be used as a method of measurement. Ultrasound examinations cannot be reproduced in their entirety for independent review at a later date and, because they are operator dependent, it cannot be guaranteed that the same technique and measurements will be taken from 1 assessment to the next. If new lesions are identified by ultrasound in the course of the study, confirmation by CT or MRI is advised. If there is concern about radiation exposure at CT, MRI may be used instead of CT in selected instances.

11.10.2.4 Endoscopy, Laparoscopy

The utilization of these techniques for objective tumor evaluation is not advised. However, such techniques may be useful to confirm complete pathological response when biopsies are obtained or to determine relapse in trials where recurrence following complete response (CR), or surgical resection is an endpoint.

11.10.2.5 Tumor markers

Tumor markers alone cannot be used to assess response. If markers are initially above the upper normal limit, they must normalize in a subject with a radiological CR for a subject to be considered a CR.

11.10.2.6 Cytology, Histology

These techniques can be used to differentiate between partial response (PR) and CR in rare cases if required by protocol (for example, residual lesions in tumor types such as germ cell tumors, where known residual benign tumors can remain).

When effusions are known to be a potential adverse effect of treatment (eg, with certain taxane compounds or angiogenesis inhibitors), the cytological confirmation of the

neoplastic origin of any effusion that appears or worsens during treatment can be considered if the measurable tumor has met criteria for response or stable disease (SD) in order to differentiate between response (or SD) and progressive disease.

11.10.2.7 FDG-PET

While fluorodeoxyglucose - positron emission tomography (FDG-PET) response assessments need additional study, it is sometimes reasonable to incorporate the use of FDG-PET scanning to complement CT scanning in assessment of progression (particularly possible 'new' disease). New lesions on the basis of FDG-PET imaging can be identified according to the following algorithm:

- Negative FDG-PET at baseline, with a positive FDG-PET at follow-up is a sign of progressive disease (PD) based on a new lesion.
- No FDG-PET at baseline and a positive FDG-PET at follow-up: If the positive FDG-PET at follow-up corresponds to a new site of disease confirmed by CT, this is PD. If the positive FDG-PET at follow-up is not confirmed as a new site of disease on CT, additional follow-up CT scans are needed to determine if there is truly progression occurring at that site (if so, the date of PD will be the date of the initial abnormal FDG-PET scan). If the positive FDG-PET at follow-up corresponds to a pre-existing site of disease on CT that is not progressing on the basis of the anatomic images, this is not PD.

11.10.3 Lesion Evaluation

11.10.3.1 Baseline documentation of "Target" and "Non-target" lesions

11.10.3.1.1 Target Lesions

- All measurable lesions up to a maximum of 2 lesions per organ and 5 lesions in total, representative of all involved organs should be identified as target lesions and recorded and measured at baseline.
- Target lesions should be selected on the basis of their size (lesions with the longest diameter) and suitability for accurate repeated measurements. All other measurable lesions will be followed as non-target lesions.
- Lymph nodes are considered 1 organ, thus a maximum of 2 measurable lymph nodes may be identified as target lesions.
- A sum of the diameters (longest for non-nodal lesions, short axis for nodal lesions) for all target lesions will be calculated and reported as the baseline sum of diameters. The baseline sum of diameters will be used as reference by which to characterize objective tumor response.

11.10.3.1.2 Non-Target Lesions

- All other lesions (or sites of disease) including pathological lymph nodes should be identified as non-target lesions and should be recorded at baseline. These lesions should be followed as "present," "absent," "unequivocal progression," or "not evaluable" throughout the study. In addition, it is possible to record multiple non-target lesions involving the same organ as a single item on the case report form (eg, "multiple enlarged pelvic lymph nodes" or "multiple liver metastases").

11.10.4 Response Criteria

Table 11-3. Evaluation of Target Lesions

Complete Response (CR)	Disappearance of all target non-nodal lesions. Any target lymph node must have reduction in short axis to < 10 mm, NOT total disappearance.
Partial Response (PR)	At least a 30% decrease in the sum of the diameters of target lesions, taking as reference the baseline sum of diameters.
Progressive Disease (PD)	At least a 20% increase in the sum of the diameters of target lesions, taking as reference the smallest sum on study (this includes the baseline sum if that is the smallest on study). In addition to the relative increase of 20%, the sum must also demonstrate an absolute increase of at least 5 mm. If a subject is missing lesion data at a disease assessment and yet progressive disease criteria is met despite the missing data, the subject will be classified as PD.
Stable Disease (SD)	Neither sufficient shrinkage to qualify for PR nor sufficient increase to qualify for PD.
Not Evaluable (NE)	When inadequate or no imaging/measurement is done at a particular time point, the subject's response is not evaluable (NE) at that time point.

Table 11-4. Evaluation of Non-target Lesions

Complete Response (CR)	Disappearance of all non-nodal non-target lesions and normalization of tumor marker level. All non-target lymph nodes must be non-pathological in size (< 10 mm short axis).
Non-CR/Non-PD	Persistence of 1 or more non-target lesions(s) and/or maintenance of tumor marker level above the normal limits.
Progressive Disease (PD)	Unequivocal progression of existing non-target lesions ^a . If a subject is missing lesion data at a disease assessment and yet unequivocal progression is met despite the missing data, the subject will be classified as PD.
Not Evaluable (NE)	When inadequate or no imaging is done at a particular time point, the subject's response is not evaluable (NE) at that time point.

^a To achieve "unequivocal progression" on the basis of the non-target disease, there must be an overall level of substantial worsening in non-target disease such that, even in presence of stable disease (SD) or partial response (PR) in target disease, the overall tumor burden has increased sufficiently to merit discontinuation of therapy. A modest "increase" in the size of 1 or more non-target lesions is usually not sufficient to qualify for unequivocal progression status.

11.10.5 Evaluation of Best Overall Response

The subject's best response assignment will depend on the findings of both target and non-target disease and will also take into consideration the appearance of new lesions and confirmation of response. Best overall response (BOR) will be based on all post-baseline disease assessments that occur prior to the initiation of subsequent anticancer treatment. At least 5 weeks from the **date of randomization** must elapse without radiological disease progression to meet the minimum criteria for SD duration in order to assign a BOR of SD. In general, subjects not classifiable under the RECIST 1.1

response categories due to inadequate data or early death will be classified as non-evaluable (NE) for BOR but will be counted in the denominator of all response rate calculations.

Table 11-5. Time Point Overall Response

Target Lesions	Non-target Lesions	New Lesions	Overall Response
Subjects with Target (\pm Non-target) Disease			
CR	CR or NA	No	CR
CR	Non-CR/non-PD or NE	No	PR
PR	CR or Non-CR/Non-PD or NE or NA	No	PR
SD	CR or Non-CR/Non-PD or NE or NA	No	SD
PD	Any	Any	PD
Any	PD	Any	PD
Any	Any	Yes	PD
NE	CR or Non-CR/Non-PD or NE or NA	No	NE
Subjects with Non-target Disease Only			
NA	CR	No	CR
NA	Non-CR/Non-PD	No	SD (Non-CR/Non-PD) ^a
NA	CR or Non-CR/Non-PD	NE	SD (Non-CR/Non-PD) ^a
NA	PD	Any	PD
NA	Any	Yes	PD
NA	NE	No	NE

CR = complete response; NE = not evaluable; PD = progressive disease; PR = partial response;

RECIST v1.1 = Response Evaluation Criteria in Solid Tumors version 1.1; SD = stable disease.

^a Per RECIST v1.1, "SD (Non-CR/Non-PD)" is preferred over "SD" for Non-target disease since SD is increasingly used as endpoint for assessment of efficacy in some trials so to assign this category when no lesions can be measured is not advised.

Table 11-6. Best Overall Response (BOR) When Confirmation of Complete Response (CR) and Partial Response (PR) Required

Overall Response First Time Point	Overall Response Second Time Point	BOR
CR	CR	CR
CR	PR	SD, PD or PR ^a
CR	SD	SD provided minimum criteria for SD duration met, otherwise, PD
CR	PD	SD provided minimum criteria for SD duration met, otherwise, PD
CR	NE	SD provided minimum criteria for SD duration met, otherwise, NE
PR	CR	PR
PR	PR	PR
PR	SD	SD
PR	PD	SD provided minimum criteria for SD duration met, otherwise, PD
PR	NE	SD provided minimum criteria for SD duration met, otherwise, NE
NE	NE	NE

CR = complete response; NE = not evaluable; PD = progressive disease; PR = partial response; SD = stable disease.

^a If a CR is truly met at first time point, then any disease at a subsequent time point (see Confirmation section below for timing), even disease meeting PR criteria relative to baseline, makes the disease PD at that point (since disease must have reappeared after CR). Best response would depend on whether minimum duration for SD was met. However, sometimes "CR" may be claimed when subsequent scans suggest small lesions were likely still present and in fact that subject had PR, not CR at the first time point. Under these circumstances, the original CR should be changed to PR and the best response is PR.

11.10.6 Special Notes on Response Assessment

- Target lesions that become "too small to measure" – While on study, all lesions (nodal and non-nodal) recorded at baseline should have their measurements recorded at each subsequent evaluation, even when very small (eg, 2 mm). However, sometimes lesions or lymph nodes which are recorded as target lesions at baseline become so faint on CT scan that the radiologist may not feel comfortable assigning an exact measure and may report them as being 'too small to measure'. When this occurs, it is important that a value be recorded on the case report form. If it is the opinion of the radiologist that the non-lymph node lesion has likely disappeared, the measurement should be recorded as 0 mm. If the lesion is believed to be present and is faintly seen but too small to measure, a default value of 5 mm should be assigned (Note: It is less likely that this rule will be used for lymph nodes since they usually have a definable size when normal and are frequently surrounded by fat such as in the retroperitoneum; however, if a lymph node is believed to be present and is faintly seen but too small to measure, a default value of 5 mm should be assigned in this circumstance as well). This default value is derived from the 5 mm CT slice thickness (but should not be changed with varying CT slice thickness). The measurement of these lesions is potentially non-reproducible, therefore providing this default value will prevent false responses or progressions

based upon measurement error. To reiterate, however, if the radiologist is able to provide an accurate measure, that should be recorded, even if it is below 5 mm.

- New lesions – The term “new lesion” always refers to the presence of a new finding that is definitely tumor. If a new lesion is identified via a modality other than CT or MRI, CT or MRI confirmation is recommended unless the new lesion is deemed unequivocally tumor. New findings that are not definitively tumor but may be benign (infection, inflammation, etc,) are not selected as new lesions, until that time when the review is certain they represent tumor.
 - If a new lesion is equivocal, for example because of its small size, continued therapy and follow-up evaluation will clarify if it represents truly new disease. If additional imaging confirms there is definitely a new lesion, then progression should be declared using the date of the initial scan.
 - A lesion identified on a follow-up study in an anatomical location that was not scanned at baseline is considered a new lesion and will indicate disease progression, regardless of any response that may be seen in target or non-target lesions present from baseline.
- Any locoregional therapy not allowed per protocol
 - Any subject receiving locoregional therapy not allowed in the protocol while on study that directly affects 1 or more of the target lesions selected at baseline will be considered to be non-evaluable at all disease assessments that occur on or after the date of locoregional therapy with the exception of disease progression. However, if a lesion was completely resected where pathology was benign the subject will still be evaluable for response with 0 dimension reported.
 - If locoregional therapy was performed on a non-target lesion, that lesion will always be assessed as present unless pathology was benign.
- Lesions that split or coalesce on treatment - When non-nodal lesions "fragment," the longest diameters of the fragmented portions should be added together to calculate the target lesion sum and identified as a fragment of the original lesion. Similarly, as lesions coalesce, a plane between them may be maintained that would aid in obtaining maximal diameter measurements of each individual lesion. If the lesions have truly coalesced such that they are no longer separable, the vector of the longest diameter in this instance should be the maximal longest diameter for the "coalesced lesion".
- “Symptomatic deterioration” alone does not qualify as objective progression. If objective progression was not previously documented, then every effort should be made to document objective progression even after discontinuation of treatment.
- In some circumstances it may be difficult to distinguish residual disease from scar or normal tissue. When the evaluation of CR depends on this determination, it is recommended that the residual lesion be further investigated by fine needle aspirate/biopsy, to confirm the CR status.
- If a lesion disappears and reappears at a subsequent time point it should continue to be measured. However, the patient’s response at the point in time when the lesion reappears will depend upon the status of his/her other lesions. For example, if the patient’s tumor had reached a CR status and the lesion reappeared, then the patient would be considered PD at the time of reappearance. In contrast, if the tumor status was a PR or SD and 1 lesion which had disappeared then reappears, its maximal diameter should be added to the sum of the remaining lesions for a calculated response: in other words, the reappearance of an apparently ‘disappeared’ single

lesion amongst many which remain is not in itself enough to qualify for PD: that requires the sum of all lesions to meet the PD criteria.

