6.1.6 Excluded Treatments, Medical Devices, and/or Procedures During Study Period

The following treatments and/or procedures are excluded within the timeframes specified during the study:

- Other investigational agents, devices (other than those specified in the protocol) and procedures are prohibited while on study treatment.
- Anticancer therapies other than those specified in the protocol are prohibited while on study treatment.
- Radiation therapy
 - Exception: Radiation therapy for symptom control (eg, bone metastasis) or brain metastasis treatment may be allowed after discussion with the medical monitor. The radiation therapy should not include the thoracic field and must have been completed at least 7 days before the subsequent dose of tarlatamab.
- Immunosuppressive agents with the exception of those required by protocol, treatment for adverse events, CNS metastases, corticosteroid replacement therapy or unless agreed upon by the investigator and medical monitor.
- During tarlatamab treatment: Live and live-attenuated vaccines are prohibited for the duration of tarlatamab treatment.
 - Live viral non-replicating vaccine (eg, Jynneos for Monkeypox infection) is allowed when administered > 3 days before or > 3 days after a tarlatamab infusion.
 - Seasonal influenza vaccines for injection are generally killed virus vaccines and are allowed when administered > 3 days before or > 3 days after a tarlatamab infusion. However, intranasal influenza vaccines (eg, Flu - Mist[®]) are live attenuated vaccines, and are not allowed at any time during tarlatamab treatment.
 - Vaccinations for COVID-19 (SARS-CoV-2 vaccination) are generally not live or live-attenuated and are allowed when administered > 3 days before or > 3 days after a tarlatamab infusion.
- After completion of tarlatamab treatment: Live and live-attenuated vaccines are prohibited for a further **60** days after last dose.
- Vaccination exclusions, restrictions, and precautions for SOC therapies are based on regional prescribing information or institutional guidelines (if not addressed in prescribing information).

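### Read literally, the Appendix 10 rule for a non-target lesion given non-permitted local therapy leaves no way to score its unequivocal progression, in conflict with Table 11-4

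*Protocol*

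**What the plan says.** Four parts of Appendix 10 of the protocol (RECIST 1.1) bear on this point.

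- **Section 11.10.6, parent bullet.** The rules on local therapy sit under "Any locoregional therapy not allowed per protocol".
- **Section 11.10.6, target lesions.** A subject whose target lesion received such therapy is non-evaluable at assessments "on or after the date of locoregional therapy with the exception of disease progression".
- **Section 11.10.6, non-target lesions.** "If locoregional therapy was performed on a non-target lesion, that lesion will always be assessed as present unless pathology was benign".
- **Sections 11.10.3.1.2 and 11.10.4.** On non-target lesions: "These lesions should be followed as 'present,' 'absent,' 'unequivocal progression,' or 'not evaluable' throughout the study". Table 11-4 then defines non-target PD as "Unequivocal progression of existing non-target lesions". Its footnote adds that "there must be an overall level of substantial worsening in non-target disease".

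Table 11-5 turns non-target PD into overall PD. Section 3 makes investigator-assessed PFS a key secondary endpoint. It censors PFS at the last evaluable assessment before new anti-cancer therapy. Section 9.4.2.2 leaves the detailed censoring rules to the SAP.

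**The concern.** The non-target sentence has a sound core: a lesion that has been irradiated or removed should not count as gone and so help to produce a false complete response. That purpose needs only a bar on the status of absence. The sentence goes further. It prescribes one status without limit of time and names one exception, benign pathology. Taken at its word, it also bars unequivocal progression, which Table 11-4 would call PD on the same scan.

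The drafters wrote a progression exception for target lesions in the sub-bullet directly above. Its absence here invites the inference that none was meant.

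At stake is the dating of progression in an open-label trial with investigator assessment. PFS is tested after OS in the controlled hierarchy, and DOR uses the same progression date. For an affected subject the error can only make the event later or lose it.

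**Working it through.** The plan has no figure to reproduce: no count of subjects expected to receive non-permitted local therapy is given, and the design values for events, HR and power are redacted. The check is mainly a comparison of texts, for one case: a non-target lesion receives non-permitted local therapy and later progresses unequivocally, with no target PD and no new lesion.

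1. **Statuses available.** Section 11.10.3.1.2 gives four: present, absent, unequivocal progression, not evaluable. The first and third are separate entries.
2. **Status under Section 11.10.6.** Present, unless pathology was benign. Progression is not among the exceptions.
3. **Non-target response if step 2 is followed.** A persisting lesion is Non-CR/Non-PD in Table 11-4. With a target response of PR or SD, Table 11-5 gives overall PR or SD.
4. **Non-target response under Table 11-4 read alone.** Unequivocal progression is PD, and Table 11-5 gives overall PD.
5. **Result.** The same scan gives no event at step 3 and a PFS event at step 4. Nothing in Appendix 10 says which text prevails.
6. **Comparison with a target lesion.** In the same situation the target-lesion sub-bullet still scores PD, so the two neighbouring rules treat progression differently.

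**Illustrative size.** Because the rates are unknown, the following rests wholly on assumptions: exponential PFS, SOC median 4 months, true HR 0.70, administrative censoring at 12 months. A randomly chosen share of each arm has its event time delayed by 6 weeks (42 / 30.4 = 1.38 months) or 12 weeks (84 / 30.4 = 2.76 months). With 1,000,000 simulated subjects per arm, the Cox HR without delay is 0.699. Change = (HR with delay / 0.699) - 1, computed before rounding:

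| Affected, tarlatamab vs SOC | 6-week delay | 12-week delay |
|---|---|---|
| 1% vs 0% | -0.2% | -0.5% |
| 5% vs 0% | -1.2% | -2.3% |
| 5% vs 2% | -0.7% | -1.3% |
| 2% vs 2% | 0.0% | +0.1% |
| 1% vs 2% | +0.3% | +0.5% |

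The sign follows the arm with more affected subjects, and the documents do not indicate which arm that would be. A 6-week delay is one scheduled scan interval. It is not a minimum: Section 8.3.1 allows extra imaging, and death or progression elsewhere can come sooner.

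**The case against.** **The sentence means only that the lesion is not to be called absent.** The benign-pathology exception supports this, as does the companion sentence that records a resected benign target lesion as zero: the contrast drawn is between still there and gone. Table 11-4 does not exclude treated lesions, and its footnote judges non-target disease as a whole. This is a plausible reading and may well be the intended one. A reader might infer that progression can never be scored; that is too strong, because target PD, a new lesion, or worsening of other non-target disease still gives overall PD. But the protocol does not state the benign purpose, and the footnote does not settle the case in which the treated lesion drives the worsening.

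**PFS may already be censored.** If non-permitted local therapy counts as new anti-cancer therapy, the lesion's later status does not matter for PFS. That would remove the PFS consequence, but no section says that it counts. The supplied SAP is an integrated safety plan without PFS rules, and the Site Imaging Manual is not among the documents. The target-lesion rule also scores progression after the therapy, which presupposes that those assessments are still used.

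**Scope.** A reader might infer that the rule also catches permitted radiation, since Section 6.1.6 says "Radiation therapy for symptom control (eg, bone metastasis) or brain metastasis treatment may be allowed after discussion with the medical monitor" and the non-target sentence does not repeat the restriction. The parent bullet limits it to therapy that is not allowed, so permitted radiation falls outside. Palliative treatment under Section 6.1.7 follows a first progression whose date is already fixed for PFS and DOR.

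**Shared CRF entries.** A reader might also infer that treating one lesion freezes every lesion recorded with it, because "it is possible to record multiple non-target lesions involving the same organ as a single item on the case report form". The rule speaks of the treated lesion alone, and nothing extends it to the others.

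**Conclusion.** The conflict is real and narrow. As written, the non-target sentence and Table 11-4 give different answers for a treated lesion that progresses unequivocally, and a literal reader of Section 11.10.6 would delay or miss the event.

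That consequence requires all of the following: local therapy the protocol does not allow, given to a non-target lesion; later progression resting on that lesion; no target PD and no new lesion; an investigator who applies the sentence literally; and, for PFS, no prior censoring for the therapy. The number of subjects is probably small, though the documents give no count. OS is unaffected.

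A reader might infer a bias of the PFS hazard ratio in favour of tarlatamab. The documents do not support that. The one-way error holds for each affected subject, but the direction for the HR depends on which arm has more of them. The range of -2.3% to +0.5% illustrates scale under assumed rates and is not an estimate for this trial.

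**What to change.** Reword the non-target sub-bullet of Section 11.10.6 along these lines: *that lesion will be assessed as present and not as absent, with the exception of unequivocal progression, which is still scored as PD, unless pathology was benign*. This keeps the guard against a false complete response and brings the rule into line with Table 11-4 and with the target-lesion rule.

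In the study's efficacy SAP, state whether local therapy that the protocol does not allow counts as new anti-cancer therapy for PFS censoring.

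The cost is one clause in Appendix 10, a matching line in the Site Imaging Manual if it repeats the rule, and one sentence in the SAP. No new scans or data are needed.
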